1. STUDY SUMMARY

1.1. Introduction

Periodontitis is a widely diffused infectious disease. Over 700 million people worldwide are supposed to suffer from it, in different degrees, although only 10-15% of the population is affected from severe forms.

The tooth supporting structures may be lost with different progression rates, depending on individual susceptibility, and may lead to edentulism early in life.

If diagnosed on time, treatment is able to reduce the clinical signs and the microbiological biofilm related to the disease.

Traditionally the first step of periodontitis treatment aims to disrupt the sub-gingival biofilm and to re-establish a healthier microbiological environment. This is commonly done by a combined manual and power-driven (ultrasonic or piezo-electric) debridement of the pocket by scaling and root-planing (SRP) associated with effective supra-gingival plaque control.

Periodontal indices that are associated with periodontitis are the increase of probing pocket depth (PPD), loss of clinical attachment (CAL) and bleeding on probing (BOP). SRP is able to reduce these indices to a certain degree although changes following treatment may be less acceptable by the patients, mainly the recession of the gingival margin (REC) and the increase in dentinal hypersensitivity (SEN).

Recently an air-abrasive system for supra- and sub-gingival debridement has been introduced, for the treatment of periodontally affected teeth.

1.2 Background information on Air-Polishing and Perio-Flow EMS

In the past few years indications for the use of the air polishing technology have been expanded from supragingival use (airflow) to subgingival air polishing (perioflow) by the development of new low-abrasive glycine-based powders (GPAP) and devices with a subgingival nozzle. Several studies on the subgingival use of air polishing have been completed. During the Europerio 7 Congress in Vienna a consensus conference on mechanical biofilm management took place aiming to review the current evidence from the literature on the clinical relevance of the subgingival use of air polishing and to make practical recommendations for the clinicians. (Sculean et al. 2013).

The latest development of a specially designed nozzle for subgingival air-polishing devices led to a reduction of the working pressure along with an air jet directed perpendicularly to the root surface. Since none of the published studies reported any adverse events related to the use of subgingival air-polishing devices, it was suggested that for the removal of supra- and subgingival dental biofilms this treatment regime may be superior to hand instrumentation, particularly with respect to patient comfort, dental hard tissue loss, and time efficiency. Recently, a new low abrasive erythritol powder (EPAP) with comparable physical properties to GPAP was introduced for subgingival air polishing. Erythritol, a non-toxic, chemically neutral, and completely water-soluble polyol is widely used as an artificial sweetener and as a food additive. Due to its comparable particle size to that of glycine and its promising chemical characteristics allowing the binding of antiseptic substances, it was recently suggested to be suitable for subgingival biofilm removal. Additionally, recently published data demonstrated an inhibitory effect of erythritol to some periodontopathogenic bacteria such as *Porphyromonas gingivalis*. Very recent data indicate that subgingival air polishing with EPAP resulted in short-term clinical outcomes comparable to SRP. Moreover, the use of EPAP yielded superior outcomes to hand instrumentation in terms of patient comfort and time efficiency.

1.3 Rationale for clinical study of Air-Polishing and Perio-Flow for the treatment of periodontitis.

So far the first treatment of severe generalized periodontitis is based on the biofilm removal, from the dental roots in the supra- and the sub-gingival environment, with the use of power-driven and hand instrumentation. This instrumentation, although proven to be successful, leads to substantial discomfort to the patients and to unpleasant gingival recessions. It is, therefore, of utmost importance to develop methods optimized for therapy with the aim to reduce these problems and to maintain the same successful healing as with previously described instrumentation.

1.4 Study design

This will be a prospective, single-masked, randomized clinical trial.

1.5 Study period

01.01.2017-31.12.2018

2. HYPOTHESIS AND STUDY OBJECTIVES

2.1 Null hypothesis and alternate hypothesis

2.1.1 H₀:

There will be no significant difference in reduction in parameters of periodontitis after debridement with Ultrasonic and Air-abrasive (Test treatment) instrumentation neither 6 weeks, 12 weeks and 24 weeks post therapy as compared with baseline.

There will be a significant difference in reduction in parameters of periodontitis after Test treatment at 6 weeks, 12 weeks and 24 weeks post therapy in favour of Control treatment.

2.1.1 H_A:

There will be a significant difference in reduction in parameters of periodontitis after debridement with Ultrasonic and Air-abrasive (Test treatment) instrumentation neither 6 weeks, 12 weeks and 24 weeks post therapy as compared with baseline.

There will be no significant difference in reduction in parameters of periodontitis after Test treatment Tr 6 weeks, 12 weeks and 24 weeks post therapy as compared with Control treatment.

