2.2 Primary Objective

To assess the clinical efficacy of Ultrasonic and Air-abrasive (Test treatment) instrumentation used as root debridement for treatment of severe generalized periodontitis. Primary end-point is pocket closure (PPD \leq 4mm).

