3.2 Examinations

Clinical examinations are to be made six weeks, at 12, 24, 36 and 52 weeks after initial therapy (i.e. the terminal evaluation is performed 12 months after initial (baseline) therapy and 9 months after the maintenance therapy).

PPD, REC, CAL, BOP, will be recorded at 6 sites (mesio-buccaly, buccaly, disto-buccaly, disto-palataly, palataly, mesio-palataly) around each tooth using a UNC- PCP 15 periodontal probe (Hu-Friedy), rounding up the measure at the nearest millimeter. Bleeding on probing is assessed at all teeth (6 sites/tooth) using dichotomous scoring within 30 seconds following probing of the pocket. Plaque for the full dentition, will also be assessed using dichotomous scoring. Radiographs will be taken at baseline and at 6 months after therapy.

Microbiological samples will be collected from the 2 deepest pockets in each quadrant with sterile

size 40 paper points and pooled in a transferring vial (4 samples/patient/examination). Sites to be collected will be isolated with cotton rolls. Supra-gingival plaque from the tooth surface will be removed with sterile curettes and thereafter air-dried. A n°40 sterile paper-point will be inserted in the depth of the pocket and removed after 10 sec, both from the vestibular and from the palatal side. Samples will be transferred into a sterile eppendorf containing suitable transport fluid and then transported to the microbiological laboratory for processing.

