4.3 WITHDRAWAL CRITERIA

A patient will be discontinued from the study under the following circumstances:

1. Progression in bone loss at teeth or other complication such as pronounced inflammation more than at study start (i.e., puss or abscesses).
2. Change in status with respect inclusion/ exclusion criteria such as pregnancy or psychological illness.

3. Intake of antibiotic medications or any local antiseptics during the length of the clinical trial.

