7.1. SAMPLE SIZE

Sample size for primary outcome (proportion of PPD<4mm) was computed through simulation assuming a non-inferiority trial with 2x2 crossover design for proportions. Data were simulated (B=1000 simulations) assuming three random intercepts (subject, tooth and site) and a within subject random slope (the within subject treatment effect). Variance estimates for the random effects were computed from existing data on a similar setting. Assuming a significance level of 5%, a tolerance margin of 10% a sample size of N=32 subjects will provide a 80% power.

Considering potential drop outs after phase I randomization to treatment phase (phase I) and maintenance phase (phase II) will be performed in a two step procedure. Subjects will be randomized to a AB scheme with varying sequence of treatment administration to the two split-mouth areas (or maintenance therapy). The seed used for randomization is 2640.

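### Section 2.1 makes a non-significant difference from control the alternative hypothesis, with no margin, although section 7.1 sizes the primary outcome as non-inferiority with a 10% margin

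*Combined protocol and SAP*

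**What the plan says.** Section 2.1 of the combined protocol and SAP gives two null and two alternative statements. The first pair compares the test treatment with baseline. The second pair compares it with control:

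- Null: a significant difference "after Test treatment at 6 weeks, 12 weeks and 24 weeks post therapy in favour of Control treatment".
- Alternative: "There will be no significant difference in reduction in parameters of periodontitis after Test treatment Tr 6 weeks, 12 weeks and 24 weeks", as against control.

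Both pairs refer to periodontitis parameters in general at three visits. Neither names the primary endpoint and neither gives a margin.

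Section 2.2 names the endpoint: "Primary end-point is pocket closure", defined as PPD ≤4 mm. Section 7 uses the same cut-off and describes two analyses, a within-patient difference in proportions and a site-level GLMM.

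Section 7.1 states: "Sample size for primary outcome (proportion of PPD<4mm) was computed through simulation assuming a non-inferiority trial with 2x2 crossover design for proportions". It continues: "Assuming a significance level of 5%, a tolerance margin of 10% a sample size of N=32 subjects will provide a 80% power". The simulation was run "assuming three random intercepts (subject, tooth and site) and a within subject random slope". The margin appears nowhere else in the available text. Section 7.2 is only a heading in this copy.

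**The concern.** The hypotheses and the sample size describe different tests. A non-inferiority trial puts a deficit at least as large as the margin under the null and rejects it when the confidence limit excludes that deficit. Section 2.1 instead puts a significant result under the null and a non-significant one under the alternative. A non-significant difference may mean that the treatments are close, or only that the trial is imprecise. The less precise the trial, the easier it is to satisfy 2.1 as written. A margin rule behaves the other way: lost precision costs power but leaves the error rate alone.

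Two further features of 2.1 do not help. The baseline pair says nothing about test against control. A significant advantage for test fits neither of the two control statements.

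The comparison with control carries the trial's conclusion, because section 1.3 aims to keep the healing achieved by conventional instrumentation while reducing its drawbacks. Two readers could reach opposite conclusions from the same primary result.

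The endpoint to which the margin applies is also written two ways: ≤4 mm in sections 2.2 and 7, <4 mm in 7.1.

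**Working it through.** **Inputs.** From section 7.1: N=32, 5% level (sidedness not stated), 10% margin (scale not stated), 80% power. No closure rates, variance components or dropout rate are given.

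**The plan's own figure.** N=32 came from a simulation whose inputs are not given, so it can be neither reproduced nor refuted. The following back-solves from it. Assumptions: absolute 10-point margin, true difference zero for sizing, normal approximation for the within-patient difference. Results are for sizing at one-sided 5%, with one-sided 2.5% in brackets.

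- SE = 0.10/(z_α + z_0.80) = 0.10/(1.645 + 0.8416) = 0.0402 [0.10/(1.960 + 0.8416) = 0.0357]
- SD = SE × √32 = 0.2275 [0.2019]

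These SDs return N=32 by construction, so this is not a confirmation.

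**Chance of success when test is truly 10 points worse, one visit.** The true deficit is 0.10/SE = 2.4865 [2.8016] standard errors.

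- Non-significant, two-sided 5%: Φ(1.960 − 2.4865) = 0.299 [Φ(1.960 − 2.8016) = 0.200]; the other tail is negligible.
- Non-significant, one-sided 5%: Φ(1.645 − 2.4865) = 0.200 [Φ(1.645 − 2.8016) = 0.124]
- Margin rule: 0.05 [0.025]

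**All three visits.** The same rules were applied to 2,000,000 simulated trivariate normal results, with between-visit correlation 0.5 to 0.9.

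| Rule met at a true 10-point deficit | One visit | All three visits |
|---|---|---|
| Non-significant, two-sided 5% | 30% [20%] | 10-21% [5-13%] |
| Non-significant, one-sided 5% | 20% [12%] | 5-13% [2-7%] |
| Margin rule | 5% [2.5%] | 0.5-2.5% [0.2-1.1%] |

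**When non-significance is the laxer rule.** At one visit, non-significance accepts observed deficits below z_test × SE, and the margin rule accepts those below margin − z_α × SE. Non-significance is therefore laxer when margin/SE < z_test + z_α. Since power = Φ(margin/SE − z_α), this means power below Φ(z_test): 95% for a one-sided 5% test, 97.5% for a two-sided one. The stated 80% is inside both limits, whatever the size of the margin.

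**Observed results, one visit.** Non-significance accepts deficits below 1.960 × SE = 7.9 [7.0] points two-sided, or 1.645 × SE = 6.6 [5.9] one-sided. The margin rule accepts only those below 10 − z_α × SE = 3.4 [3.0]. An observed 5-point deficit would pass 2.1 as worded and fail the margin rule.

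**Effect of precision.** With 24 patients and the same SD, two-sided non-significance at one visit rises from 30% to 42% [20% to 32%], while the margin rule stays at 5% [2.5%]. With no true difference, non-significance has probability 95% at any sample size, against 80% for the margin rule at N=32.

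**Sensitivity to SD.** For SD 0.15 to 0.30, two-sided non-significance at one visit runs from 3.5% to 53%. Those SDs imply power of 98% down to 60% [96% to 47%], so the ends do not fit the stated 80%. At SD 0.15 non-significance is not clearly laxer (3.5% against 5% [2.5%]).

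**Endpoint.** Section 3.2 has depths recorded by "rounding up the measure at the nearest millimeter". On whole millimetres, <4 means 3 or less, so the two definitions differ by every site recorded as 4 mm. The documents do not say how many such sites to expect.

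**The case against.** The strongest reply is that 2.1 is a narrative hypothesis and not the decision rule. It names no test, level or primary endpoint. The only passage that gives the primary outcome an inferential frame is 7.1, which says non-inferiority, and the null in 2.1 points in the same direction. If a full section 7.2 holds a confidence-limit rule, what remains is loose wording. This stands as far as it goes. A reader might infer that the primary analysis will declare success on a non-significant result, but neither section 7 nor 7.1 says so. Nor can the empty 7.2 be read as proof that the plan has no rule. What survives is the conflict between 2.1 and 7.1, which needs correcting whatever 7.2 contains.

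The size also depends on the reading. A reader might take 30% as the error of the trial. That figure is for a two-sided test at one visit, whereas 2.1 names three visits and has a one-directional null. The closest reading, one-sided at all three, gives 5-13% [2-7%]. Its low end is about what a one-visit margin rule accepts, although at matched visits the margin rule is stricter. Requiring the baseline change and several parameters as well would lower the chance of success further; this is not modelled. Reading 2.1 as failed only by significance at every visit would raise it.

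A reader might also infer that withdrawals under section 4.3 would greatly inflate false success. The criterion, "Progression in bone loss at teeth or other complication such as pronounced inflammation more than at study start", does not refer to which half of the mouth is affected, so it does not imply that patients with the largest test deficits are removed. Loss selected that way would bias a margin rule too. Handling of withdrawals, and of the maintenance randomised at the week-12 recall, are separate matters and add nothing to the weight of this point.

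The <4 mm in 7.1 may be a typing or text-extraction slip, since the other two places agree. It still needs confirming against the simulation.

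**Conclusion.** The point holds. As written, 2.1 makes absence of a significant difference from control the alternative hypothesis, with no margin, and so conflicts with the non-inferiority sizing in 7.1. The available text links neither analysis in section 7 to the margin. This rests on the wording alone.

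The probabilities are illustrations that depend on the back-solved SD and the other assumptions above. The direction is firmer: at the stated 80% power, and compared at the same visits, non-significance is the laxer rule under each reading tabulated. Nothing here shows that N=32 is wrong. On the visible text this should be fixed; a stronger rating would depend on the content of section 7.2, which cannot be seen.

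**What to change.** Restate the comparison with control in 2.1 for pocket closure, as H0: test minus control ≤ −margin and HA: test minus control > −margin. Then:

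- Use the 10% margin of 7.1 on the scale and at the sidedness used in the simulation, and state both.
- Name one primary visit, and as primary the one analysis (patient-level difference, or GLMM result expressed on the margin's scale) for which the 80% power was simulated. Report the other as supportive.
- Conclude non-inferiority only if the lower confidence limit lies above −margin.
- Remove absence of a significant difference as a success condition, and treat other visits and parameters as secondary.
- Reconcile PPD ≤4 mm (2.2 and 7) with PPD <4 mm (7.1), and confirm which one the simulation used.
- Check the result against any full text of section 7.2.

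The cost is protocol and SAP wording and a few lines of analysis code. It calls for no change to N and no added patients or procedures.

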2.2 Primary Objective

To assess the clinical efficacy of Ultrasonic and Air-abrasive (Test treatment) instrumentation used as root debridement for treatment of severe generalized periodontitis. Primary end-point is pocket closure (PPD \leq 4mm).

2.3 Secondary Objectives

To assess other clinical indices measured for periodontitis (REC,CAL, BOP, PI; Schiff Index).

To assess the changes in the sub-gingival microbial biofilm after treatment.

To assess the time spent by the therapist in treatment.

To assess patient subjective appraisal of morbidity (i.e., pain) and preference of both treatments used (VAS scale).

To assess safety of treatment by evaluating the occurrence of adverse events

3 Interventions

3.1 Treatment procedure

The initial debridement is performed with local anesthesia as needed. Randomly assigned quadrants will be treated by FM-EPAPT or SRP.

Maintenance procedure will be performed at 12, 24 and 36 weeks. Each quadrant in both active treatment groups, will be randomly maintained by either a FM-EPAPT procedure or by ultrasonic debridement.

3.2 Examinations

Clinical examinations are to be made six weeks, at 12, 24, 36 and 52 weeks after initial therapy (i.e. the terminal evaluation is performed 12 months after initial (baseline) therapy and 9 months after the maintenance therapy).

PPD, REC, CAL, BOP, will be recorded at 6 sites (mesio-buccaly, buccaly, disto-buccaly, disto-palataly, palataly, mesio-palataly) around each tooth using a UNC- PCP 15 periodontal probe (Hu-Friedy), rounding up the measure at the nearest millimeter. Bleeding on probing is assessed at all teeth (6 sites/tooth) using dichotomous scoring within 30 seconds following probing of the pocket. Plaque for the full dentition, will also be assessed using dichotomous scoring. Radiographs will be taken at baseline and at 6 months after therapy.

Microbiological samples will be collected from the 2 deepest pockets in each quadrant with sterile

size 40 paper points and pooled in a transferring vial (4 samples/patient/examination). Sites to be collected will be isolated with cotton rolls. Supra-gingival plaque from the tooth surface will be removed with sterile curettes and thereafter air-dried. A n°40 sterile paper-point will be inserted in the depth of the pocket and removed after 10 sec, both from the vestibular and from the palatal side. Samples will be transferred into a sterile eppendorf containing suitable transport fluid and then transported to the microbiological laboratory for processing.

4 STUDY METHODS

4.1 INCLUSION CRITERIA

In addition to general medical condition and history, patients can be included if they meet the following conditions:

1. Age: 30-75 with diagnosis of severe generalized periodontitis.
2. At least 5 teeth per quadrant and a minimum of 6 sites per quadrant with PPD \geq 5 mm and loss of CAL \geq 3mm. (Sites with PPD \geq 10 mm will be excluded from measurement but not from treatment).
3. Eligible for treatment in an outpatient dental clinic (ie, ASA I and II).
4. Signed Informed Consent obtained prior to start.
5. Psychological appropriateness.
6. Consent to complete all follow-up visits.

4.2 EXCLUSION CRITERIA

In addition to general conditions and history, patients should be excluded if they meet any of the

following conditions:

1. Was receiving medications known to induce gingival hyperplasia.
2. Had uncontrolled diabetes (HbA1c > 6.5).
3. Was receiving systemic antibiotics < 3 months prior to intervention.
4. Were pregnant or lactating.
5. Any condition or current treatment for any condition, which in the opinion of the investigator and/or consulting physician, may constitute an unwarranted therapeutical risk.
6. Presence of psychological characteristics such as inappropriate attitude or motivation which, in the opinion of the investigator, are incompatible with the risks involved with the treatment.
7. Unwillingness to undergo treatment
8. Ongoing or previous radiotherapy to the head-neck region
9. Ongoing or previous chemotherapy
10. Systemic long-term corticosteroid treatment
11. Patients taking anticoagulants
12. Heavy smokers more then 10 cigarettes per day

4.3 WITHDRAWAL CRITERIA

A patient will be discontinued from the study under the following circumstances:

1. Progression in bone loss at teeth or other complication such as pronounced inflammation more than at study start (i.e., puss or abscesses).
2. Change in status with respect inclusion/ exclusion criteria such as pregnancy or psychological illness.

3. Intake of antibiotic medications or any local antiseptics during the length of the clinical trial.

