4.9 POSTOPERATIVE FOLLOW-UP PROCEDURES

All postoperative evaluations will be recorded on the Postoperative Report Form 6, 12, 24, 36 and 52 weeks post therapy. Furthermore radiographs will be taken after 12 months to exclude progression in bone loss.

At the 12, weeks recall Each quadrant in both active treatment groups, will be randomly maintained by either a FM-EPAPT procedure or by ultrasonic debridement.

Clinical complications such as infection, pain, etc. will be recorded during all postoperative follow-up visits, should they occur.

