7. STATISTICAL ANALYSIS

Data will be analyzed both at patient level focusing on a within patient difference between two

proportions (proportion of PPD \leq 4mm in the two treatments) as well as considering the response at site level fitting a GLMM model with binomial link function and multilevel structure matching the design.

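### Section 4.3 stops follow-up of both sides of the mouth when disease worsens or any antibiotic or antiseptic is taken, which can shift later results modestly towards non-inferiority

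*Combined protocol and SAP*

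**What the plan says.** Section 4.3 lists when a patient is discontinued from the study. Item 1 is "Progression in bone loss at teeth or other complication such as pronounced inflammation more than at study start", with pus or abscess as examples. Item 3 is "Intake of antibiotic medications or any local antiseptics during the length of the clinical trial", with no restriction on the reason. The unit withdrawn is the patient, and under section 1.6 each patient carries both treatments.

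The primary endpoint is pocket closure, PPD of 4 mm or less (section 2.2). Section 7 plans a patient-level comparison of the two closure proportions and a site-level analysis "fitting a GLMM model with binomial link function and multilevel structure matching the design". Section 7.1 frames the trial as non-inferiority: "Assuming a significance level of 5%, a tolerance margin of 10% a sample size of N=32 subjects will provide a 80% power". Drop-outs appear there only as the reason for randomizing treatment and maintenance in two steps ("Considering potential drop outs after phase I randomization to treatment phase"). The supplied text names no analysis set, no scoring of withdrawn patients and no visit term in the model.

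Two provisions bear on the remedy. Patients are included on "Consent to complete all follow-up visits" (section 4.1), and section 4.9 says that complications "will be recorded during all postoperative follow-up visits, should they occur".

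Radiograph timing differs between sections. Section 3.2 says "Radiographs will be taken at baseline and at 6 months after therapy". Section 4.9 places a film after 12 months and gives its purpose as ruling out progressive bone loss.

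**The concern.** Item 1 describes treatment failure. Item 3 covers any drug intake, and some of it may be given for a failing site. Leaving the study can therefore depend on the outcome. Because the two sides are paired within a patient, failure on one side also removes the other side's later readings.

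If both sides fail equally often, the rule costs only precision. If the test side is truly worse, the worse side of a failing patient is more often the test side, so the patients who leave tend to be those with larger test-side deficits. An analysis of those who remain then looks more favourable to the test treatment. A truly worse test side is the situation a non-inferiority trial has to detect, and with 32 patients each loss counts: 2 of 32 is 6%.

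Only readings after withdrawal are affected. Nothing in section 4.3 says that readings already taken are discarded.

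**Working it through.** **1. The plan's own figure.** N = 32 came from a simulation whose variance components and closure rate are not given, and the sidedness of the 5% level is not stated. It cannot be reproduced. The SD of the within-patient difference that would give 80% power at no true difference can be back-solved:

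SD = margin × √N / (z for alpha + z for power)

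- One-sided 5%: 0.10 × √32 / (1.645 + 0.842) = 0.5657 / 2.487 = 0.2275.
- One-sided 2.5%: 0.5657 / (1.960 + 0.842) = 0.2019.

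**2. Model.** From the documents: N = 32, margin 0.10, split-mouth pairs. Assumed: closure 0.70 on control and 0.60 on test (true difference at the margin). Each side is its mean plus a shared patient effect (SD 0.12, varied from 0 to 0.18) plus a side effect of SD 0.161, since 0.161 × √2 ≈ 0.2275. The test is a paired non-inferiority t-test on remaining patients only. With all 32 patients and no true difference, simulated power is 78%, close to the stated 80%.

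**3. False non-inferiority with 2 of 32 lost, nominal one-sided 5%, shared SD 0.12**

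| Who leaves | Rate | Shift in estimate (points) |
|---|---|---|
| At random | 4.9% | 0.0 |
| Risk proportional to unclosed sites, either side | 5.0% | 0.0 |
| Imperfect trigger on the worse side, correlation 0.3 / 0.5 / 0.7 | 5.4% / 6.0% / 6.3% | 0.2 or more, below 0.8 |
| The 2 patients with the worst single side | 7.5% (6.9% to 9.0% over shared SD 0 to 0.18) | 0.8 |
| Risk proportional to unclosed sites, test side only | 6.0% | 0.4 |
| The 2 patients with the worst test side | 11.0% (9.6% to 13.3%) | 1.6 |
| The 2 largest test-minus-control deficits (extreme bound) | 20% | 2.8 |
| The 2 patients with the worst control side | 2.4% | reversed |

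For the worst-single-side case, losing 1 patient gives 6.4% and losing 4 gives 9.7%. At one-sided 2.5% with 2 lost, the rates are 2.6% (proportional, either side), 4.2% (worst single side) and 6.1% (worst test side).

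**4. Using an earlier visit.** If a likelihood model also uses a visit before withdrawal, with between-visit correlation 0.5 / 0.7 / 0.9, the worst-single-side rate falls from about 7.5% to 6.7% / 6.1% / 5.4%. The worst-test-side rate falls from about 11% to 9.0% / 7.9% / 6.1%.

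**5. Which visits are exposed.** Pus, abscess and drug intake can act at any visit. Bone loss needs a film. With the 6-month film of section 3.2, the 24-week readings are already in, so only weeks 36 and 52 can be affected. If only the 12-month film of section 4.9 is used, it falls at the final 52-week visit and no later scheduled reading is lost. On either reading, the 6-, 12- and 24-week results named in the hypotheses (section 2.1) are untouched by the bone-loss trigger.

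**6. Keeping everyone.** With all 32 retained, one tooth in ten on the failed side scored not closed, and correlation 0.7, the rates are 4.8% (worst single side) and 4.5% (worst test side). Power at no true difference is 77.3%, against 78.0% with all 32 scored as observed. This run does not model the effect of a systemic antibiotic on the other sites.

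**The case against.** The strongest case against has five parts.

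- **The rule is side-neutral.** Item 1 refers to teeth without naming a side, and section 4.6 keeps the examiner unaware of which quadrants had the test procedure. A reader might take the 10% to 13% rates, or the 20% bound, as the size of the problem. The documents do not support that, because those rates require selection on the test side, or on the test-minus-control deficit, alone. This part stands, and it limits the relevant range to the either-side cases.
- **Item 3 is not a rescue rule.** A reader might infer that it withdraws patients for rescue antibiotics. It covers intake for any reason, and intake unrelated to the mouth acts like random loss, with no inflation. Only the part given for a failing site matters, and its frequency is unknown.
- **Bone loss is a weak route.** A reader might infer that it distorts the 36- and 52-week results. That depends on which film is used. The only film that the protocol ties to bone loss is at 12 months, and then no later visit is lost.
- **Earlier visits may be modelled.** Section 7.1 simulates a site-level random intercept, which for a binary outcome suggests repeated readings. The text does not say so, but it makes the remaining-patients figures an upper version of each case. Maintenance is also re-randomized by quadrant from week 12 (sections 3.1 and 4.9), so a fixed side deficit is a simplification at late visits.
- **Absence is uncertain.** Section 7.2 is a heading without text as supplied, and Table 1 is an attachment that was not supplied. An analysis-set rule could sit in either, so I do not count their silence against the plan.

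The stated rule in section 4.3 survives all five: it stops follow-up for reasons that can include failure, and it does so for both sides at once.

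**Conclusion.** The point holds in a limited form, and the change should be made. Withdrawal under items 1 and 3 can depend on outcome and removes both sides' later readings. If the test side truly fails more often, results can move modestly towards non-inferiority: about 5% to 8% false non-inferiority against a nominal 5% with 2 of 32 lost (up to 9% over the assumed shared SDs), or a shift of at most 0.8 points at shared SD 0.12 against a 10-point margin. Modelling earlier visits reduces this.

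A reader might conclude that the rule biases this trial towards non-inferiority. The documents do not show that. The direction depends on which side fails more: equal failure costs only precision, and control-driven loss works against the test treatment.

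The size rests on assumed values for the number lost, the trigger, 70% control closure, the SDs, one-sided 5% and analysis of remaining patients only. Confidence is medium.

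**What to change.** **Section 4.3.** Let patients who meet item 1 or item 3 receive whatever care they need, but keep them in follow-up at all scheduled visits. Record the side and teeth that failed, and the date and reason for any antibiotic or antiseptic.

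**Section 7.** Analyse all randomized patients. Count sites on teeth rescued or extracted for failure as not closed from that visit on. Use observed readings for the patient's other sites. As a sensitivity analysis, exclude these patients or their post-antibiotic readings. State whether the GLMM includes visit.

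**Cost.** A few sentences, one case report form field and a little more analysis work. No extra patients or visits are needed, since consent to all visits and recording of complications are already in place. The simulated loss of power is under one point (78.0% − 77.3% = 0.7). The real downside is that a systemic antibiotic acts on both sides, so readings taken after it may dilute a difference; the sensitivity analysis is there to show how much that matters.
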